9.0 ADVERSE EVENTS

The prompt reporting of adverse events is the responsibility of each investigator engaged in clinical research, as required by Federal Regulations. Adverse events must be described and graded using the terminology and grading categories defined in the NCI's Common Terminology Criteria for Adverse Events (CTCAE), Version 5.0. The CTCAE is available at ctep.cancer.gov/protocolDevelopment/electronic_applications/ctc.htm. Attribution to protocol treatment for each adverse event must be determined by the investigator and reported on the required forms. Please refer the NCI Guidelines: Adverse Event Reporting Requirements for further details on AE reporting procedures.

Clinician graded CTCAE is the AE safety standard. PRO-CTCAE items are to complement CTCAE reporting. Patients will respond to PRO-CTCAE items, but no protocol directed action will be taken. The PRO-CTCAE patient-completed booklet for this protocol can be downloaded from the CIRB Approved Documents tab on the CTSU website. PRO-CTCAE is not intended for expedited reporting, real time review, or safety reporting. All dose interruptions and treatment modifications will be guided by clinician interpreted CTCAE. PRO-CTCAE should not be used for determining dose delays or dose modifications or any other protocol directed action.

9.1 Routine Adverse Event Reporting

Adverse event data collection and reporting, which are required as part of every clinical trial are done to ensure the safety of patients enrolled in the studies as well as those who will enroll in future studies

using similar agents. Adverse events are reported in a routine manner at scheduled times according to the study calendar in [Section 5.0](#).

9.1.1 Solicited adverse events

The following adverse events are considered "expected" and their presence/absence should be solicited, and severity graded, at baseline and for each cycle of treatment. Symptomatic adverse events reported by patients through PRO-CTCAE are not safety reporting and may be presented with other routine Adverse Event data.

CTCAE v5.0 Term	CTCAE v5.0 System Organ Class (SOC)	PRO-CTCAE Term
Neutrophil count decreased	Investigations	N/A
Platelet count decreased	Investigations	N/A
Diarrhea	Gastrointestinal Disorders	Diarrhea
Colitis	Gastrointestinal Disorders	Diarrhea, Abdominal Pain
Rash maculo-papular	Skin and subcutaneous tissue disorders	Rash
Hyperglycemia	Metabolism and nutrition disorders	N/A
Electrocardiogram QT corrected interval prolonged	Investigations	N/A

9.2 CTCAE Routine Reporting Requirements

In addition to the solicited adverse events listed in [Section 9.1](#), the following table outlines the combinations of time points, grades and attributions of AEs that require routine reporting to the Alliance Statistics and Data Center. Questions about routine reporting should be directed to the Data Manager.

Combinations of CTCAE Grade & Attribution Required for Routine AE Data Submission on Case Report Forms (CRFs)

Attribution	Grade 1	Grade 2	Grade 3	Grade 4	Grade 5
Unrelated			a	a	a
Unlikely			a	a	a
Possible			a, b	a, b	a, b
Probable			a, b	a, b	a, b
Definite			a, b	a, b	a, b

- a) **Adverse Events: Other CRF** - Applies to AEs occurring between registration and within 30 days of the patient's last treatment date, or as part of the Clinical Follow-Up Phase.
- b) **Adverse Events: Late CRF** - Applies to AEs occurring greater than 30 days after the patient's last treatment date.

9.3 Expedited Adverse Event Reporting (CTEP-AERS)

Investigators are required by Federal Regulations to report serious adverse events as defined in the table below. The descriptions and grading scales found in the NCI Common Terminology Criteria for Adverse Events (CTCAE) version 5 will be utilized for AE reporting. The CTCAE is identified and

located on the CTEP website at: ctep.cancer.gov/protocolDevelopment/electronic_applications/ctc.htm. All appropriate treatment areas should have access to a copy of the CTCAE. All reactions determined to be “reportable” in an expedited manner must be reported using the Cancer Therapy Evaluation Program Adverse Event Reporting System (CTEP-AERS).

For further information on the NCI requirements for SAE reporting, please refer to the ‘NCI Guidelines for Investigators: Adverse Event Reporting Requirements’ document published by the NCI.

Note: All deaths on study require both routine and expedited reporting regardless of causality. Attribution to treatment or other cause should be provided.

9.3.1 Late Phase 2 and Phase 3 Studies: Expedited Reporting Requirements for Adverse Events that Occur on Studies under an IND/IDE within 30 Days of the Last Administration of the Investigational Agent/Intervention^{1,2}

FDA REPORTING REQUIREMENTS FOR SERIOUS ADVERSE EVENTS (21 CFR Part 312)

NOTE: Investigators **MUST** immediately report to the sponsor (NCI) **ANY** Serious Adverse Events, whether or not they are considered related to the investigational agent(s)/intervention (21 CFR 312.64)

An adverse event is considered serious if it results in **ANY** of the following outcomes:

- 1) Death
- 2) A life-threatening adverse event
- 3) An adverse event that results in inpatient hospitalization or prolongation of existing hospitalization for ≥ 24 hours
- 4) A persistent or significant incapacity or substantial disruption of the ability to conduct normal life functions
- 5) A congenital anomaly/birth defect.
- 6) Important Medical Events (IME) that may not result in death, be life threatening, or require hospitalization may be considered serious when, based upon medical judgment, they may jeopardize the patient or subject and may require medical or surgical intervention to prevent one of the outcomes listed in this definition. (FDA, 21 CFR 312.32; ICH E2A and ICH E6).

ALL SERIOUS adverse events that meet the above criteria **MUST** be immediately reported to the NCI via electronic submission within the timeframes detailed in the table below.

Hospitalization	Grade 1 Timeframes	Grade 2 Timeframes	Grade 3 Timeframes	Grade 4 & 5 Timeframes
Resulting in Hospitalization ≥ 24 hrs		10 Calendar Days		24-Hour 5 Calendar Days
Not resulting in Hospitalization ≥ 24 hrs	Not required		10 Calendar Days	

NOTE: Protocol specific exceptions to expedited reporting of serious adverse events are found in the Specific Protocol Exceptions to Expedited Reporting (SPEER) portion of the CAEPR

Expedited AE reporting timelines are defined as:

- “24-Hour; 5 Calendar Days” - The AE must initially be submitted electronically within 24 hours of learning of the AE, followed by a complete expedited report within 5 calendar days of the initial 24-hour report.
- “10 Calendar Days” - A complete expedited report on the AE must be submitted electronically within 10 calendar days of learning of the AE.

¹Serious adverse events that occur more than 30 days after the last administration of investigational agent/intervention and have an attribution of possible, probable, or definite require reporting as follows:

Expedited 24-hour notification followed by complete report within 5 calendar days for:

- All Grade 4, and Grade 5 AEs

Expedited 10 calendar day reports for:

- Grade 2 adverse events resulting in hospitalization or prolongation of hospitalization
- Grade 3 adverse events

²For studies using PET or SPECT IND agents, the AE reporting period is limited to 10 radioactive half-lives, rounded UP to the nearest whole day, after the agent/intervention was last administered. Footnote “1” above applies after this reporting period.

Effective Date: May 5, 2011

9.3.2 Expedited AE reporting timelines defined

- “24 hours; 5 calendar days” – The investigator must initially report the AE via CTEP-AERS \leq 24 hours of learning of the event followed by a complete CTEP-AERS report \leq 5 calendar days of the initial 24-hour report.
- “10 calendar days” - A complete CTEP-AERS report on the AE must be submitted \leq 10 calendar days of the investigator learning of the event.

Any medical event equivalent to CTCAE grade 3, 4, or 5 that precipitates hospitalization (or prolongation of existing hospitalization) must be reported regardless of attribution and designation as expected or unexpected with the exception of any events identified as protocol-specific expedited adverse event reporting exclusions (see below).

Any event that results in persistent or significant disabilities/incapacities, congenital anomalies, or birth defects must be reported via CTEP-AERS if the event occurs following treatment with an agent under an IND.

Use the NCI protocol number and the protocol-specific patient ID provided during trial registration on all reports.

9.3.3 Adverse Events of Special Interest in Pembrolizumab Studies

Adverse events of special interest for this study include the following:

- Cases of potential drug-induced liver injury that include an elevated ALT or AST in combination with either an elevated bilirubin or clinical jaundice, as defined by Hy's law:
 - Treatment-emergent ALT or AST $> 3 \times$ ULN in combination with total bilirubin $> 2 \times$ ULN
 - Treatment-emergent ALT or AST $> 3 \times$ ULN in combination with clinical jaundice
- Data related to a suspected transmission of an infectious agent by the study drug (STIAMP), as defined below:

Any organism, virus, or infectious particle (e.g., prion protein transmitting transmissible spongiform encephalopathy), pathogenic or non-pathogenic, is considered an infectious agent. A transmission of an infectious agent may be suspected from clinical symptoms or laboratory findings that indicate an infection in a patient exposed to a medicinal product. This term applies only when a contamination of the study drug is suspected

The Pembrolizumab Events of Special Interest Are:

- Systemic lupus erythematosus
- Events suggestive of hypersensitivity, infusion-related reactions, cytokine-release syndrome, macrophage activating syndrome, hemophagocytic lymphohistiocytosis
- Nephritis
- Ocular toxicities (e.g., uveitis, retinitis, optic neuritis)
- Grade ≥ 2 cardiac disorders (e.g., atrial fibrillation, myocarditis, pericarditis)
- Vasculitis
- Autoimmune hemolytic anemia
- Severe cutaneous reactions (e.g., Stevens-Johnson syndrome, dermatitis bullous, toxic epidermal necrolysis)

9.3.4 Additional Instructions or Exclusions to CTEP-AERS Expedited Reporting Requirements

All adverse events reported via CTEP-AERS (i.e., serious adverse events) should also be forwarded to your local IRB.

Alliance A032002 uses a drug under a CTEP IND. The reporting requirements for investigational agents under a CTEP IND should be followed for all agents (any arm) in this trial.

Treatment expected adverse events include those listed in Section 10.0 and in the package insert. CTEP-AERS reports should be submitted electronically.

Exclusions

≤ Grade 4 hematosuppression and hospitalization resulting from such do not require CTEP-AERS, but should be submitted as part of study results.

Grade 1-3 nausea or vomiting and hospitalization resulting from such do not require AERS reporting, but should be reported via routine AE reporting

Grade 3 nausea or vomiting does not require AERS reporting, but should be reported via routine AE reporting.

Death

Death due to progressive disease should be reported as Grade 5 “Disease progression” in the system organ class (SOC) “General disorders and administration site conditions.” Evidence that the death was a manifestation of underlying disease (e.g., radiological changes suggesting tumor growth or progression: clinical deterioration associated with a disease process) should be submitted.

Any death occurring within 30 days of the last dose, regardless of attribution to the investigational agent/intervention requires expedited reporting within 24 hours.

Any death occurring greater than 30 days after the last dose of the investigational agent/intervention requires expedited reporting within 24 hours only if it is possibly, probably, or definitely related to the investigational agent/intervention.

Pregnancy loss and neonatal death

Pregnancy loss is defined in CTCAE as “Death in utero.” Any Pregnancy loss should be reported expeditiously, as Grade 4 “Pregnancy loss” under the Pregnancy, puerperium and perinatal conditions SOC. A Pregnancy loss should NOT be reported as a Grade 5 event under the Pregnancy, puerperium and perinatal conditions SOC, as currently CTEP-AERS recognizes this event as a patient death.

A neonatal death should be reported expeditiously as Grade 4, “Death neonatal” under the General disorders and administration SOC.

New Malignancies

All new malignancies must be reported via CTEP-AERS whether or not they are thought to be related to either previous or current treatment. All new malignancies should be reported, i.e. solid tumors (including non-melanoma skin malignancies), hematologic malignancies, myelodysplastic syndrome/acute myelogenous leukemia, and in situ tumors.

Whenever possible, the CTEP-AERS reports for new malignancies should include tumor pathology, history or prior tumors, prior treatment/current treatment including duration, any associated risk factors or evidence regarding how long the new malignancy may have been present, when and how the new malignancy was detected, molecular characterization or cytogenetics of the original tumor (if available) and of any new tumor, and new malignancy treatment and outcome, if available.

Secondary Malignancy

A secondary malignancy is a cancer caused by treatment for a previous malignancy (e.g., treatment with investigational agent/intervention, radiation or chemotherapy). A secondary malignancy is not considered a metastasis of the initial neoplasm.

CTEP requires all secondary malignancies that occur following treatment with an agent under an NCI IND/IDE be reported via CTEP-AERS. Three options are available to describe the event:

- Leukemia secondary to oncology chemotherapy (e.g., acute myelocytic leukemia [AML])
- Myelodysplastic syndrome (MDS)
- Treatment-related secondary malignancy

Any malignancy possibly related to cancer treatment (including AML/MDS) should also be reported via Rave.

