13.7 Secondary Analysis Plans

A key secondary analysis will be to repeat the primary analysis that defines a tumor response by central review using iRECIST criteria.

For the secondary time-to-event endpoints, stratified Cox models will be used to compare the outcomes between the two treatment groups. This includes PFS and OS. The subgroup analyses will be done using a stratified Cox model that includes the treatment arm assignment as an explanatory variable and a separate model will be generated for each level for the subgroup of interest. The results will be summarized with a forest plot displaying the estimate of the hazard ratio and corresponding 95% confidence interval.

The rates of treatment discontinuation at one year will be summarized with a binomial point estimate and corresponding 95% confidence interval by arm. The denominator will be all patients randomized to the treatment arm and who are still alive and progression-free at one year and the numerator will be the number of patients who are alive and progression-free at one year and discontinued the protocol

treatment prior to one year. A comparison between the rates will be performed with a chi-square test or a Fisher's exact test if the assumptions of the chi-square test are violated.

Adverse events will be summarized with frequencies and relative frequencies. The maximum grade for an AE will be recorded for each patient by treatment arm. The number (percent) of patients that experience each observed adverse event will be summarized by treatment arm. In addition, the proportion of patients that experience a grade 3+, grade 4+, and grade 5 adverse event will be summarized as the number and percent of patients by treatment arm. The primary summary will be regardless of attribution. We will also do an analogous summary of the adverse events that were deemed at least possibly related to treatment.

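### Progression deaths are coded as Grade 5 adverse events and stay in the all-attribution grade 3+, 4+ and 5 proportions in Section 13.7, so the by-arm toxicity tallies mix in disease mortality

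*Combined protocol and SAP*

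**What the plan says.** Section 9.3.4 (Death) instructs sites: "Death due to progressive disease should be reported as Grade 5", with the term *Disease progression*. Section 9.3 adds: "All deaths on study require both routine and expedited reporting regardless of causality".

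Section 13.7 plans several displays of CTCAE data by arm:

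- A per-term table: "The number (percent) of patients that experience each observed adverse event will be summarized by treatment arm".
- Aggregate tallies: "the proportion of patients that experience a grade 3+, grade 4+, and grade 5 adverse event will be summarized" by arm.
- The attribution rule: "The primary summary will be regardless of attribution".
- A second view: "We will also do an analogous summary of the adverse events that were deemed at least possibly related to treatment".

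No sentence removes *Disease progression* from the aggregate tallies.

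Section 9.2 sets what reaches the routine forms. Grade 3 to 5 events judged unrelated or unlikely go only on the *Other* form, which "Applies to AEs occurring between registration and within 30 days of the" last treatment date, "or as part of the Clinical Follow-Up Phase". The follow-up phase in that clause is not defined. The *Late* form, for events more than 30 days after last treatment, takes only events at least possibly related.

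**The concern.** Objective 2.2.4 is to assess adverse events with and without radiotherapy. Death from any cause is already the overall survival endpoint in Section 13.2.2. When a death from the cancer is also a Grade 5 adverse event, it enters the grade 3+, 4+ and 5 proportions together, and the between-arm difference reflects both toxicity and disease mortality.

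Some of these deaths will be captured even on the narrowest reading of Section 9.2. Sections 7.1 and 12.1 let treatment continue past progression while the patient still benefits, so a patient can die of progression within 30 days of the last dose.

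The direction of the distortion depends on survival. Longer survival in Arm B offsets part of a real toxicity excess. Shorter survival in Arm B makes radiotherapy look more toxic than it is. Either way, a reader of the primary summary cannot tell how much of the difference is toxicity.

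**Working it through.** The documents give no expected adverse event rate and no count of progression deaths, so there is no plan figure to reproduce. The calculation below is an illustration.

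**Assumed inputs**

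- *t*, the proportion with another grade 3+ event: 25% in Arm A and 40% in Arm B, a true excess of +15 points.
- *q*, the proportion with a progression death captured in the adverse event data: 10% to 20%, standing for deaths near the end of treatment.
- Toxicity and progression death are independent within an arm.

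**Formula.** Observed grade 3+ = 1 − (1 − t)(1 − q).

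| q in A / B | Arm A | Arm B | Difference (points) |
|---|---|---|---|
| 0 / 0 | 25.0% | 40.0% | +15.0 |
| 15% / 15% | 1 − 0.75×0.85 = 36.3% | 1 − 0.60×0.85 = 49.0% | +12.8 |
| 20% / 20% | 1 − 0.75×0.80 = 40.0% | 1 − 0.60×0.80 = 52.0% | +12.0 |
| 15% / 10% | 36.3% | 1 − 0.60×0.90 = 46.0% | +9.8 |
| 20% / 12% | 40.0% | 1 − 0.60×0.88 = 47.2% | +7.2 |
| 10% / 15% | 1 − 0.75×0.90 = 32.5% | 49.0% | +16.5 |
| 12% / 20% | 1 − 0.75×0.88 = 34.0% | 52.0% | +18.0 |

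The same formula applies to grade 4+, with lower *t*.

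**Dependence on independence.** If no patient had both events, the rates would add: equal *q* would leave +15, 15% / 10% would give (40 + 10) − (25 + 15) = +10, and 20% / 12% would give (40 + 12) − (25 + 20) = +7. If every patient with a progression death had already had another grade 3+ event, nothing would change. The attenuation under equal mortality therefore comes from the overlap being larger in the more toxic arm.

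**Grade 5.** Assume toxic deaths of 1% vs 5% and captured progression deaths of 10% vs 6%. One cause per death gives 1 + 10 = 11% vs 5 + 6 = 11%; the independence formula gives 10.9% vs 10.7%. About 10/11 = 91% of Arm A's figure is disease death, and a 4-point excess in toxic death is no longer visible. With 10% in both arms, the independence formula gives 10.9% vs 14.5%, which keeps 3.6 of the 4 points.

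**Can the per-term table undo this?** Not for grade 3+ or 4+. In the 15% / 15% case, subtracting the *Disease progression* line from Arm A gives 36.3 − 15 = 21.3%, not 25%. The gap is the overlap, 0.25 × 0.15 = 3.75 points, which no planned table shows.

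**The case against.** The strongest reply is that Section 13.7 already separates these events. *Disease progression* gets its own by-arm line in the per-term table, and a related-only summary is planned. The CTCAE tallies are descriptive, with no test and no stated decision resting on them. Part of this stands. Because each death has one recorded cause, a reader can largely recover the Grade 5 proportion from the per-term line. The grade 3+ and 4+ proportions cannot be recovered that way. The related-only summary depends on attribution by investigators (Section 9.0) in an open-label trial (Section 13.1).

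A second reply is that removing the term outright would weaken a conservative display. Calling a death progressive disease is itself an open-label judgement, and a toxic death could be misfiled there. This stands, and it is why the tallies should be shown both ways.

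A reader might infer something stronger: that the whole summary mainly measures survival and could reverse a true excess. Take the 10.3-month median in Section 1.1, exponential survival, an assumed hazard ratio of 0.70, and every death to 36 months counted. Deaths are then 1 − 0.5^(36/10.3) = 91% vs 1 − 0.5^(36×0.70/10.3) = 82%. Grade 3+ reads 1 − 0.75×0.089 = 93% vs 1 − 0.60×0.183 = 89%, or −4 points; at hazard ratio 1.0 it reads 93% vs 95%. The documents do not support this reading. Section 9.2 collects unrelated events mainly to 30 days after last treatment, and its follow-up clause is undefined. Section 9.3 gives no time limit for deaths on study, but Section 9.3.4 limits expedited reporting of deaths after 30 days to those at least possibly related. Section 12.3.1 asks only for survival information after progression. Disease death alone would exceed half of Arm A's grade 3+ rate only if *q* were above t/(1 − t) = 0.25/0.75 = 33%.

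**Conclusion.** The concern holds as a defect in how the tallies are defined. As written, every progression death that reaches the adverse event data counts in the primary grade 3+, 4+ and 5 proportions. That includes at least those up to 30 days after last treatment; Sections 9.2 and 9.3 leave later ones open. The Grade 5 proportion may consist mostly of disease deaths.

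For grade 3+ the likely effect is moderate. Under the assumed rates and independence, a +15-point excess reads about +12 to +13 with equal progression mortality, about +7 to +10 if Arm B survives longer, and +16.5 to +18 in the mirrored cases where it survives less. Masking therefore needs better survival in Arm B, and equal mortality does not swamp the difference. The toxicity rates, captured-death rates and independence are all assumptions. The missing rule for *Disease progression* is not.

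**What to change.** Amend Section 13.7 to state that the by-arm grade 3+, 4+ and 5 proportions and the maximum-grade summaries, whatever the attribution, will be reported in two versions:

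1. Excluding the term *Disease progression*, used for the toxicity comparison.
2. Including it, as a guard against a toxic death being classed as progression.

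Add a table of deaths by cause and arm, and state one adverse event collection window that applies to both arms for all of these displays. All other terms stay in the all-attribution summary.

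The term is already coded separately, so the two versions need no new data or site work. The cost is a short addition to Section 13.7 and one extra table. Cause of death remains an open-label judgement, which the second version keeps in view. Specifying this before the analysis avoids choosing a version after the results are known.
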